15. References.....	24
16. Appendix	27
16.1 Modified Rankin Scale ²⁷	27
16.2 Glasgow Coma Scale ²⁸	28
16.3 National Institute of Health Stroke Scale ²⁹	29
16.4 Abbreviations	38

CLP-15131 Protocol Synopsis	
Registry Title:	INSIGHT: Investigation of Clot in Ischemic Stroke and Hematoma Evacuation
Primary Objectives:	The aim of the study is to collect and analyze specimen from ischemic stroke patients undergoing thrombectomy procedures and from patients undergoing minimally invasive surgery for intracranial hematoma evacuation. Clot and blood specimen will be analyzed via histology, RNA sequencing, Single Nucleotide Polymorphisms (SNPs), and proteomic analysis.
Secondary Objective:	To prospectively collect and correlate comprehensive data relating patient's clinical presentation, hospital course, and length of hospital stay to specimen histology, RNA sequencing, SNPs, and proteomic analysis.
Registry Study Design:	This will be a prospective, multi-center, registry for the collection and analysis of specimen collected from ischemic stroke thrombectomy procedures and minimally invasive interventions for intracranial hematoma evacuation utilizing the Penumbra Aspiration Pump.
Indication:	Per FDA 510(k) cleared Indication stated in the Instructions For Use. (IFU)
Registry Device:	Penumbra Aspiration Pump
Patient Population:	Up to 400 patients will be enrolled from up to 30 sites in the United States. (US) Specimen will be analyzed via histology, RNA sequencing, SNPs, and proteomics.
Study Duration:	It is anticipated that enrollment will take approximately 2 years. Each patient may be in the registry for approximately 90 days from enrollment to last optional follow-up.
Follow-up:	Follow-up assessments will occur at discharge and an optional phone visit at approximately 90 days following the procedure.
Inclusion Criteria:	
 1. ≥ 18 Years of Age 2. Frontline treatment with: 
 • Penumbra System for ischemic stroke patients eligible for mechanical thrombectomy or • Artemis Neuro Evacuation device for intracranial hematoma evacuation in patients eligible for minimally invasive surgery (MIS) 3. Extracted thrombus/embolus 4. Informed consent is obtained from either patient or legally authorized representative (LAR)
Exclusion Criteria:	
 1. Pregnancy or positive pregnancy test according to site routine practice (only required for women of childbearing potential; serum or urine acceptable) 2. Currently participating in an investigational drug or device clinical trial that may confound the ability to capture clot and/or influence clot composition.

CLP-15131 Protocol Synopsis	
Registry Title:	INSIGHT: Investigation of Clot in Ischemic Stroke and Hematoma Evacuation
	Patients in observational, natural history, and/or epidemiological studies not involving intervention are eligible.
Statistical Methods:	No formal statistical testing is planned for this study. All analyses will be descriptive and considered as hypothesis generating for future studies.

1. Introduction

Globally, cerebrovascular accidents are a leading cause of death and disability.¹ In 2013, an estimated 10.3 million new strokes were identified, of which two thirds were ischemic (incidence 99-132 per 100,000) and one third were hemorrhagic (incidence 56-65 per 100,000) or other non-ischemic cases.²

The recent publication of multiple randomized controlled trials established the efficacy of mechanical thrombectomy in treating stroke and have dramatically changed first-line treatments and recommendations for acute ischemic stroke.^{3, 4} Clinical studies have also addressed hemorrhagic stroke, for which current surgical options and therapies are more limited⁵; treatments for this stroke subtype focus on the evacuation of hematoma and removal of clot volume using minimally invasive techniques.⁶⁻⁹

Despite these rapid advances in stroke treatment, mortality remains high: ischemic strokes accounted for 3.3 million deaths in 2013, and hemorrhagic strokes for an additional 3.2 million deaths globally.² Rates of global mortality in 2013 were 57.3 per 100,000 people for ischemic stroke and 52.8 per 100,000 people for hemorrhagic stroke.¹⁰

In ischemic stroke, good clinical outcomes are often contingent on timely clot removal to attain revascularization.^{3, 11} Consequently, understanding clot characteristics could inform vital pre-treatment decisions and guide secondary prevention strategies by revealing stroke etiology.¹² Historically, data from stroke-implicated clot has been scarce, but the expansion of contemporary endovascular technologies provides an ideal opportunity to collect thrombus material for direct study.¹²

1.1 Thrombus Composition

Clots removed during endovascular procedures can differ in consistency and removability¹³, leading to an increased focus on thrombus composition as a crucial variable for improving outcomes in both AIS and minimally invasive hematoma evacuation patients. Clot age¹⁴, component ratios¹⁵, and etiology¹⁶⁻¹⁸ can each affect the structural properties of a clot, impacting success rates of thrombolytic treatments^{15, 19} and the choice of clinical intervention¹⁸.

For example, thrombus maturation results in decreased mechanical compliance due to progressive fibrin cross-linking and collagen deposition.¹⁴ These lysis-resistant fibrin clots can be more recalcitrant to endovascular treatment and are predictive of adverse patient outcomes.²⁰ By contrast, erythrocyte-rich thrombi are associated with improved efficacy of endovascular thrombectomy.²¹⁻²³ A recent study of patients undergoing intra-arterial thrombectomy with either a stent or suction device showed that clots retrieved from successful recanalization trials had a higher proportion of red blood cells (RBC) than those from non-recanalization trials; these RBC-rich clots were also associated with the presence of a hyperdense clot sign during initial brain imaging.²³

Thrombus composition can also depend on patient predisposing factors, including Diabetes mellitus, cardiovascular disease, statin use, and anticoagulant use (e.g. vitamin-K antagonists, non-vitamin K oral anticoagulants, antiplatelet agents).²⁴⁻²⁶ These conditions affect clot structure and fibrin content, indicating that patient history may become an important predictor of targeted and successful treatment strategies.

1.2 Conclusion and Rationale

This prospective study will be conducted on ischemic stroke and intracranial hematoma evacuation cases. Clot removed during endovascular therapy and minimally invasive hematoma evacuations will be collected for histological, RNA sequencing, SNPs, and proteomic analysis.

More specifically, this study will examine whether clot composition, genetic, and proteomic variables can provide insight into thrombus etiology and/or have impact on clinical outcomes in patients with outwardly similar initial presentations.

This registry is not intended to be utilized or support a labelling/indication change in the United States.

2. Risk Analysis

This study uses FDA 510(k) cleared medical devices per indication in the cleared labeling. The overall risk profile for the Penumbra Aspiration Pump is low, as the devices do not come into contact with the patient. Risk analysis was performed as part of design control requirements of the Quality System Regulation (21 CFR 820).

There are risks associated with the clot evacuation procedure and should be discussed with potential patients according to each institution's routine practice.

2.1 Risk to Patients

The primary risk in this study is a potential breach of confidentiality. To minimize the risk, all study records containing protected health information (PHI) will be de-identified and assigned a unique patient identification number. Protocols will be in place for the handling and destruction of collected specimen.

Blood collection has minimal risk and will be performed during the procedure through the existing procedural vascular access per institution routine practice.

3. Registry Overview

3.1 Study Design

This is a prospective, multicenter, registry for the collection and analysis of specimen collected from ischemic stroke thrombectomy procedures and minimally

invasive interventions for intracranial hematoma evacuation procedures utilizing the Penumbra Aspiration Pump.

Patients eligible for thrombectomy or minimally invasive surgery, and who meet the inclusion and none of the exclusion criteria will be considered for enrollment. Treatment will be per site routine practice, using FDA cleared devices.

Patients will be considered enrolled upon signed informed consent and specimen collection. Specimen collected during the procedure will be shipped to a study Core Lab(s) for analysis.

Data for each patient will be collected at the time of enrollment and at each subsequent follow-up visit. Please refer to the Schedule of Assessments (Table 1) below for details.

3.2 Study Objectives

3.2.1 Primary Objectives

- The aim of the study is to collect and analyze specimen from ischemic stroke patients undergoing thrombectomy procedures and from patients undergoing minimally invasive surgery for intracranial hematoma evacuation. Clot and blood specimen will be analyzed via histology, RNA sequencing, Single Nucleotide Polymorphisms (SNPs), and proteomic analysis.

3.2.2 Secondary Objectives

- To prospectively collect and correlate data relating patient's clinical presentation, hospital course, and length of hospital stay to specimen histology, RNA sequencing, SNPs, and proteomic analysis.

4. Study Population

Up to 400 patients will be enrolled from up to 30 sites in the United States. Specimen will be analyzed via histology, RNA sequencing, SNPs, and proteomics.

4.1 Inclusion Criteria

1. ≥ 18 Years of Age
2. Frontline treatment with:
 - Penumbra System for ischemic stroke patients eligible for mechanical thrombectomy or
 - Artemis Neuro Evacuation device for intracranial hematoma evacuation in patients eligible for minimally invasive surgery (MIS)
3. Extracted thrombus/embolus

4. Informed consent is obtained from either patient or legally authorized representative (LAR)

4.2 Exclusion Criteria

[figure not shown]
1. Pregnancy or positive pregnancy test according to site routine practice (only required for women of childbearing potential; serum or urine acceptable)
2. Currently participating in an investigational drug or device clinical trial that may confound the ability to capture clot and/or influence clot composition. Patients in observational, natural history, and/or epidemiological studies not involving intervention are eligible.

5. Study Procedures

5.1 Overview of Study Flow

Screening information will be reported in the Screening and Enrollment Log.

Figure 1: Study Flow

[^] May be obtained up to 1 calendar day post-procedure, prior to specimen shipment to Core Lab

[!] Must be shipped as quickly as possible, but no later than 72 hours post procedure

⁺ Whichever comes first

^{*} Optional Visit (conducted by phone)

5.2 Study Visits

Patients enrolled in this study will follow the visit schedule below. Procedure is considered day 0 to determine subsequent follow-up visit dates.

- Baseline Evaluation
- Procedure
- Discharge or 7 Days (whichever occurs first)
- 90 Day Follow-Up ± 14 Days (Optional phone call)

5.3 Screening and Baseline Evaluation

Patients will be clinically evaluated per site routine practice. The following information will be collected at Baseline:

- Medical History
- Demographics
- Clot/Hematoma Location
- Medications (including antiplatelet and anticoagulant use)
- The National Institutes of Health Stroke Scale (NIHSS)
- Glasgow Coma Score (GCS) – (MIS only)
- Historical (Pre-stroke) Modified Rankin Score (mRS)

5.4 Informed Consent

The Investigator or designee will obtain written informed consent from the patient or approved delegate using the current IRB approved consent form per IRB policy.

The patient or legally authorized representative (LAR) may provide informed consent up to one calendar days post-procedure.

All informed consent documents used under this protocol will be consistent with applicable elements of I.S. EN ISO 14155, Clinical investigation of medical devices for human subjects – Good Clinical Practice and 21 CFR Part 50 and will be approved by the site's reviewing IRB prior to registry initiation.

- Any modification to the sample informed consent form made by the study site must be approved by the Sponsor and the IRB before use. Each study site will provide the Sponsor with a copy of the IRB approved consent forms.
- Informed consent completion will be monitored regularly by the Sponsor.

5.5 Procedure

All procedures are to be conducted per routine practice at each study site.

The following information may be captured in the Case Report Form (CRF):

- Administration of intravenous thrombolytics (IV rtPA), Anti-coagulation agents, and medications
- Imaging times and results
 - Modified Thrombolysis in Cerebral Infarction (mTICI) scores pre and post procedure (AIS only)
 - Pre and post procedure hematoma volume (MIS only)
- Key procedural time points
- First pass to specimen extraction (AIS only)
- SAE collection

5.5.3 Specimen for Acute Ischemic Stroke Cases

Specimen will be collected during the procedure in the filter (clot catcher) by study personnel. The clot catcher is part of the single use canister for the Penumbra Aspiration Pump.

After the specimen is collected into the RNA collection tube, it is recommended to fill the RNA Clot collection tube with the fluid in the canister prior to sealing.

Prior to thrombectomy, and during flushing of the diagnostic or guide catheter, approximately 10 mL of extracranial blood should be collected from the diagnostic or guide catheter. It is recommended to allow approximately 10-15ml waste while backflushing prior to obtaining the 10ml sample. 5 mL will be placed into each of the EDT purple top collection tubes provided in the specimen collection kit.

5.5.4 Specimen for Minimally Invasive Surgery

Specimen will be collected during the procedure in the canister within the Penumbra Aspiration Pump by study personnel.

The specimen may be obtained in whole piece(s) or fragments after evacuation by the Artemis device. After the specimen is collected into the RNA collection tube it is recommended to fill the RNA Clot collection tube with the fluid in the canister prior to sealing.

Approximately 10 mL of blood should be collected from the arterial line and 5 mL will be placed into each of the EDT purple top collection tubes provided in the specimen collection kit. The blood should be collected from the arterial line around the same time as the clot evacuation.

5.6 Discharge or 7 Days (whichever occurs first)

The following assessments will be performed per site routine practice at discharge or 7 Days post procedure:

- National Institutes of Health Stroke Scale (NIHSS)
- Modified Rankin Scale (mRS)
- Glasgow Coma Score (GCS) – (MIS only)
- SAE collection

5.7 90 Day Follow-Up ±14 Days (Optional phone visit)

The following assessment will be performed per site routine practice at this optional phone visit:

- Modified Rankin Scale (mRS)

Table 1: Schedule of Assessments

ACTIVITY	Baseline Evaluation	Procedure	Discharge or 7 Days ⁶	90 Day Follow-Up ¹ (±14 Days)
Informed Consent²	X			
Medical History	X			
Demographics	X			
Medication Review	X	X		
Clot Retrieval		X		
Blood Sample Collection		X		
Hematoma Volume³		X		
NIHSS	X		X	
mTICI⁴		X		
mRS	X ⁵		X	X
GCS³	X		X	
Serious Adverse Events⁷		X	X	

¹Optional Visit (conducted by phone)

² May be obtained up to 1 calendar day post-procedure and must be obtained prior to shipment of samples

³ Minimally invasive surgery / hematoma evacuation patients only

⁴ Ischemic stroke patients from digital subtracted angiography

⁵ Historical (pre-stroke)

⁶ Whichever occurs first

⁷ The following SAEs will be collected through 7 days post procedure: Device related events, procedural related events, Symptomatic ICH (sICH) at 24 hours, symptomatic embolization of new territory (ENT) at end of procedure

6. Specimen Collection and Shipment

All specimen should be placed within the provided collection tube(s) then securely packaged in the specimen collection kit provided, and shipped to the Core Lab(s) as quickly as possible, but no later than 72 hours post procedure and after informed consent is obtained.

The study sponsor will provide specimen kits, comprised of the following components:

- Mini Sample collection tube(s) for the clot
- Sealable plastic biohazard bags
- Absorbent material
- Paraffin tape for mini sample collection tubes(s)
- Purple collection tubes for blood samples (x2)
- Return packaging for specimen shipment to the Core Lab(s)
- UN 3373, Biological substances, Category B label
- Instructions for specimen collection, packing and shipping the specimen kit

Prior to return shipment to the Core Lab(s), document the kit number for entry into the database. The samples should be packaged per the packaging and shipping instructions and must comply with the Department of Transportation (DOT), Hazardous Materials Regulations (HMR), 49 CFR Parts 171-180) and the International Airline Transport Associate (IATA) for shipping of Hazardous Materials.

Study personnel responsible for packaging and/or shipping must be trained in the packaging and shipping of Category B, biological substance, as described in the DOT/IATA division 6.2 and HMR 173.134(b)(10). Certification of training will be required for all study personnel delegated to perform specimen packaging and shipping as described in this protocol.

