8.3.3 Interim Monitoring

Conducted as needed to ensure the study site is operating in compliance with this protocol, continues to have the appropriate staff and facilities, and is correctly completing the CRFs.

The visits ensure that Investigators and their staff understand and accept their defined responsibilities, the Sponsor will maintain regular correspondence and perform periodic site visits during the course of the study to verify the continued acceptability of the facilities, compliance with the investigational plan, and maintenance of complete records. Clinical monitoring will include review of informed consent forms for enrolled patients. Informed consent, eCRFs and medical records for all enrolled patients will be made available to the Sponsor for review and collection.

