10.1 General Statistical Considerations

All statistical analyses will be descriptive in nature. Descriptive statistics will include the number of observations, mean, median, standard deviation, inter-quartile range, minimum and maximum for continuous variables and counts and percentages for discrete variables. All confidence intervals presented will be two-sided. Analyses will be conducted using SAS (SAS Institute, Cary, NC). The specific details of the planned analyses are described completely in the statistical analysis plan.

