INSIGHT: Investigation of Clot in Ischemic Stroke and Hematoma Evacuation

STATISTICAL ANALYSIS PLAN

CLP-15131

Version 3.0

Sponsor

Penumbra, Inc.
[name]
[name]
USA

Contents

1. Overview	3
2. Study objectives	3
2.1 Primary Objectives	3
2.2 Secondary Objectives	4
3. Sample size.....	4
4. Interim analysis.....	4
5. General Statistical methods.....	4
6. Patient Disposition	4
6.1 Enrolled	4
6.2 Completed.....	5
6.3 Early Termination.....	5
7. Definition of Analysis Population	5
8. Statistical Analysis	5
9. Analysis of adverse events.....	6
10. Subgroup analysis.....	6
11. Pooling across centers	7
12. Lost to follow-up and missing data	7
13. Central Core and Pathophysiology Lab.....	8
14. Changes to planned analysis	8
15. References	8
16. Revision History.....	8

1. Overview

This is a prospective, multicenter, registry for the collection and analysis of specimen collected from ischemic stroke thrombectomy procedures and minimally invasive interventions for intracranial hematoma evacuation utilizing the Penumbra Aspiration Pump. The aim of the study is to collect and analyze specimen via histology, RNA sequencing, Single Nucleotide Polymorphisms (SNPs), and proteomic analysis. This will then be correlated to comprehensive data relating to patient's clinical presentation, hospital course, and length of hospital stay. Patients eligible for thrombectomy or minimally invasive surgery, who meet the inclusion and none of the exclusion criteria will be considered for enrollment. Treatment will be per site routine practice, using FDA cleared devices. Patients will be considered enrolled upon signed informed consent and specimen collection. Up to 400 patients from up to 30 sites in the United States will be enrolled into this registry. Each site will be limited to a maximum enrollment of 60 subjects (approximately 15% of the total enrolled). It is anticipated that enrollment will take approximately 2 years. Each patient will be in the registry for up to 90 days from enrollment to last follow-up. Data for each subject will be collected at the time of enrollment, discharge or 7days (whichever comes first) and 90 Days (optional) follow-up.

2. Study objectives

This study will examine whether clot composition, genetic, and proteomic variables can provide insight into thrombus etiology and/or have impact on clinical outcomes in patients with outwardly similar initial presentations.

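### The SAP's subgroup outcome labelled NIHSS at discharge is really the discharge-or-day-7 score, and nothing ensures that its subgroup differences are adjusted for baseline NIHSS

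*Combined protocol and SAP*

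**What the plan says.** **NIHSS.** Protocol 5.3 collects NIHSS at baseline. Protocol 5.6 and Table 1 schedule it once more: "The following assessments will be performed per site routine practice at discharge or 7 Days post procedure". The heading of 5.6, the visit list in 5.2 and SAP 1 all make this the earlier of the two dates. The optional 90-day call collects mRS only. The synopsis is looser: "Follow-up assessments will occur at discharge and an optional phone visit at approximately 90 days following the procedure".

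SAP 10 lists NIHSS at discharge among its subgroup outcomes, without the 7-day limit. It promises descriptive statistics and 95% confidence intervals for each subgroup and for the difference between subgroups. Covariates and multivariate modelling follow for differences judged notable. SAP 8 separately promises exploratory multivariate analyses but names no outcome or covariate. SAP 10 also reports 90-day mortality; it does not ask for deaths before the discharge-or-day-7 visit.

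**Length of stay.** The secondary objective (protocol 3.2.2, repeated in SAP 2.2) is "To prospectively collect and correlate data relating patient's clinical presentation, hospital course, and length of hospital stay to specimen histology" and the other specimen analyses. SAP 1 says of the specimen results: "This will then be correlated to comprehensive data relating to patient's clinical presentation, hospital course, and length of hospital stay". Protocol 10.1 states: "The specific details of the planned analyses are described completely in the statistical analysis plan". SAP 8 limits that plan to clinical data and histology, which covers stay against histology, but does not name stay.

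**The concern.** The label and the data disagree. A reader of the final report would take the NIHSS result as each patient's status on leaving hospital. For longer stays it is a score at a fixed day 7, and the mix of the two kinds of score can differ between subgroups, for example between ischemic and hemorrhagic stroke.

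The adjustment rule depends on the result. If one subgroup arrives with more severe strokes, part of any later NIHSS difference is simply that severity carried forward. Imbalance can also hide a difference. Because covariates enter SAP 10 only after a notable unadjusted difference, the hidden case is the one least likely to be adjusted.

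Patients who die before the visit have no NIHSS, so the comparison is among survivors to that point. Without the count of early deaths by subgroup, a reader cannot judge how far that selection matters.

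Length of stay raises a smaller question: a variable named in the objective has no stated start, no listed dates and no named summary.

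**Working it through.** The plan gives no sample-size calculation, NIHSS variability or stay distribution, so there is no figure of its own to reproduce.

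**Step 1: which NIHSS exists.** Protocol 5.3, 5.6, 5.7 and Table 1 give NIHSS at baseline and at the discharge-or-day-7 visit only. SAP 10's outcome can therefore only be the latter.
- Discharged by day 7: the score is a discharge score and the label is right.
- Still in hospital at day 7: the score is a day-7 score and the label is wrong.

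The share in the second group is not given. Assuming 10% to 60% of the maximum 400: 0.10 × 400 = 40 and 0.60 × 400 = 240 patients.

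**Step 2: precision gained by adjustment.** Assumptions: SD 7 points, two subgroups of 200 (an even split of 400), correlation r between baseline and later NIHSS of 0.4 to 0.7.
- Unadjusted half-width: 1.96 × 7 × √(2/200) = 1.37.
- Adjusted half-width: 1.37 × √(1 − r²).

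| r | √(1 − r²) | half-width |
|---|---|---|
| 0.4 | 0.917 | 1.26 |
| 0.5 | 0.866 | 1.19 |
| 0.6 | 0.800 | 1.10 |
| 0.7 | 0.714 | 0.98 |

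The interval narrows by 8% to 29%. In this formula the percentage depends only on r, not on the SD or the split. It is approximate, because adjustment costs some precision when baseline differs between subgroups.

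**Step 3: what imbalance does.** Assume a 2-point baseline difference and a slope of later on baseline NIHSS of 0.4, 0.6 or 0.7. The amount carried into the unadjusted difference is 2 × 0.4 = 0.8, 2 × 0.6 = 1.2 or 2 × 0.7 = 1.4 points. At the upper end this is about as large as the half-width of 1.37. If the baseline-adjusted difference were 1.2 points in the opposite direction, then at slope 0.6 the unadjusted difference would be 1.2 − 1.2 = 0. Nothing notable would appear, and SAP 10 would not call for covariates.

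**Step 4: length of stay.** None of protocol 5.3 to 5.7 or Table 1 lists an admission or discharge date. Protocol 5.2 says "Procedure is considered day 0 to determine subsequent follow-up visit dates"; that fixes visit dates, not the start of stay. No stay summary is named in SAP 8.

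The effect of a 7-day limit, if there were one, was simulated under assumptions: lognormal stay from procedure, log SD 0.7, medians 5, 7 and 10 days, stay 20% longer per SD of a clot measure.

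| Stay data | rank correlation, medians 5 / 7 / 10 |
|---|---|
| complete | 0.24 / 0.24 / 0.24 |
| longer stays recorded as 7 | 0.23 / 0.22 / 0.20 |
| longer stays dropped | 0.17 / 0.15 / 0.12 |

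No text in the documents says that longer stays will be recorded as 7 or dropped.

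**The case against.** **On NIHSS.** Only one post-procedure score is scheduled and SAP 1 states the visit rule, so an analyst cannot pick the wrong variable. That is right: the fault is in what a reader is told. SAP 8's multivariate analyses carry no trigger, so it would be wrong to infer that the whole plan adjusts only after a notable difference. That also stands; but SAP 8 commits to no particular outcome or covariate, so baseline adjustment of NIHSS is still not assured. SAP 10 aims to describe the effect of baseline conditions, and unadjusted differences serve that aim. This is a reason to keep them and add the adjusted ones beside them. It also means there is no case for adjusting mTICI or the clot measures in the same way. Early deaths can show as 6 on the mRS at the same visit, and SAP 5 reports numbers of observations, but neither gives deaths by subgroup beside the NIHSS result.

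**On stay.** A reader might infer that stay beyond day 7 is not collected and the objective cannot be met. The documents do not support this. The objective itself says to collect stay, and the CRF is not among the documents. Protocol 8.3.3 says: "Informed consent, eCRFs and medical records for all enrolled patients will be made available to the Sponsor for review and collection". The visit lists are not exhaustive: smoking and COVID status, used in SAP 10, are not itemised there either. Protocol 7.5.1 runs serious adverse event collection through discharge for patients treated with RED catheters, although its text also uses a 7-day limit. Even under a cap, the assumed rank correlation hardly moves.

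**Conclusion.** The NIHSS point holds. The SAP 10 label is wrong for every patient still in hospital at day 7, and the plan does not ensure a baseline-adjusted difference for this outcome. The gain from adjustment is moderate: 8% to 29% narrower intervals, and protection against 0.8 to 1.4 points of carried-over severity for a 2-point imbalance. These sizes rest on an assumed SD of 7, 200 patients per subgroup, correlations of 0.4 to 0.7 and slopes of 0.4 to 0.7. The label and the conditional adjustment rule are matters of text and need no assumption. The registry is descriptive, so no formal test is at risk; what changes is how the subgroup estimates read.

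The stay point holds only as a minor clarification. The definition and the named analysis are missing; whether the dates are missing cannot be told from the documents. If the CRF holds both dates, no data are lost. The stay figures are illustrations only.

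**What to change.** 1. In SAP 10, rename the outcome NIHSS at discharge or day 7, and bring the synopsis wording into line with protocol 5.2.
2. For this outcome only, always present the subgroup difference and 95% confidence interval adjusted for baseline NIHSS beside the unadjusted one, whatever the size of the unadjusted difference.
3. Report by subgroup the number who died before the visit.
4. Confirm that the CRF holds admission date, actual discharge date (not limited to day 7) and discharge status, and add any that are absent. State whether stay starts at admission or at procedure.
5. Name in SAP 8 a descriptive summary of stay against histology by stroke type, with in-hospital deaths shown separately. Only if a later discharge date is truly unavailable, treat that stay as right-censored at day 7 (plus the admission-to-procedure interval if stay starts at admission), rather than recording it as 7 or leaving it out.

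Items 1 and 2 use data already collected and cost a few sentences. Item 3 needs only a count, provided death before the visit is recorded; the mRS of 6 is one route. Items 4 and 5 cost a CRF check and SAP text; if fields are missing, three chart-based entries per patient, with look-up for those already enrolled.
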